## Availability

Telaglenastat (CB-839) HCl is an investigational agent supplied to investigators by the Division of Cancer Treatment and Diagnosis (DCTD), NCI.

Telaglenastat (CB-839) HCl is provided to the NCI under a Collaborative Agreement between the Pharmaceutical Collaborator and the DCTD, NCI (see Section 13.4).

### 8.1.2 Osimertinib (AZD9291) (NSC 781254)

**Chemical Name:** N-(2-{{2-(Dimethylamino)ethyl}(methyl)amino}-4-methoxy-5-{{4-(1-methyl-1H-indol-3-yl)pyrimidin-2-yl}amino}phenyl)prop-2-enamide methanesulfonate

**Other Names:** TagrissoTM, AZD9291 mesylate

**Classification:** Epidermal growth factor receptor (EGFR) inhibitor

**Molecular Formula:** C28H33N7O2.CH4O3S      **M.W.:** 595.71 (mesylate salt)  
499.61 (free base)

**Approximate Solubility:** The solubility of osimertinib free base has been measured as 7.2 mg/mL in Simulated Gastric Fluid (pH 1.4) and 0.2 mg/mL in Fasted State Simulated Intestinal Fluid (pH 6.5).

**Mode of Action:** Osimertinib (AZD9291) is a potent, oral, irreversible, tyrosine kinase inhibitor (TKI) of epidermal growth factor receptor (EGFR) mutation-positive (EGFRm) and T790M mutation-positive forms of EGFR.

**Description:** Osimertinib mesylate is a crystalline powder.

**How Supplied:** Osimertinib (AZD9291) tablets are supplied by AstraZeneca and

distributed by the Pharmaceutical Management Branch, CTEP/DCTD/NCI. Tablets are packaged in 30-count bottles with mannitol, microcrystalline cellulose, low-substituted hydroxypropyl cellulose and sodium stearyl fumarate as inactive ingredients in the following strengths:

- 80 mg tablets: beige, oval and biconvex tablet marked with “AZ 80” on one side and plain on the reverse.
- 40 mg tablets: beige, round and biconvex tablet marked with “AZ 40” on one side and plain on the reverse.

The tablet coating contains polyvinyl alcohol, titanium dioxide, macrogol 3350, talc, ferric oxide yellow, ferric oxide red and ferric oxide black.

**Storage:** Store at room temperature 20° to 25°C (68° to 77°F), excursions permitted between 15 to 30°C (59 to 85°F).

If a storage temperature excursion is identified, promptly return osimertinib (AZD9291) to controlled room temperature and quarantine the supplies. Provide a detailed report of the excursion (including documentation of temperature monitoring and duration of the excursion) to [contact] for determination of suitability.

**Stability:** Refer to the package label for expiration.

**Route of Administration:** Take by mouth with or without food. If a dose of osimertinib (AZD9291) is missed or vomited, do not make up the missed dose and take the next dose as scheduled.

**Potential Drug Interactions:** The main metabolic pathways of osimertinib (AZD9291) are oxidation (predominantly CYP3A4) and dealkylation in vitro. Avoid concomitant use of strong CYP3A4 inducers. CYP3A4 inhibitors are not likely to affect the exposure of osimertinib (AZD9291). Based on in vitro studies, osimertinib (AZD9291) is a competitive inhibitor of CYP 3A4/5 but not CYP1A2, 2A6, 2B6, 2C8, 2C9, 2C19, 2D6 and 2E1 at clinically relevant concentrations. Osimertinib (AZD9291) is an inducer of CYP1A2. Use caution with coadministration of CYP 3A4/5 and 1A2 substrates.

Osimertinib (AZD9291) is a substrate of BCRP and P-gp but is unlikely to result in clinically relevant drug interactions. Osimertinib (AZD9291) is not a substrate of OATP1B1 and OATP1B3 and does not inhibit OAT1, OAT3, OATP1B1, OATP1B3, OCT2, MATE1 and MATE2K at clinically relevant concentrations. Based on in vitro data, osimertinib (AZD9291) is an inhibitor of BCRP and may increase the exposure of BCRP substrates. Osimertinib (AZD9291) does not inhibit P-gp at clinically relevant concentrations but has the potential to increase exposure of sensitive substrates.

Avoid use of osimertinib (AZD9291) in patients with congenital long QT syndrome. For patients with normal QT interval at the trial enrollment, avoid use of concomitant drugs that are known to prolong QT interval and use caution with drugs that may prolong QT interval. Refer to a frequently updated drug information reference and to the protocol for appropriate cardiac monitoring.

### 8.1.3 Agent Ordering and Agent Accountability

NCI-supplied agents may be requested by eligible participating Investigators (or their authorized designee) at each participating institution. The CTEP-assigned protocol number must be used for ordering all CTEP-supplied investigational agents. The eligible participating investigators at each participating institution must be registered with CTEP, DCTD through an annual submission of FDA Form 1572 (Statement of Investigator), NCI Biosketch, Agent Shipment Form, and Financial Disclosure Form (FDF). If there are several participating investigators at one institution, CTEP-supplied investigational agents for the study should be ordered under the name of one lead participating investigator at that institution.

In general, sites may order initial agent supplies when a subject is being screened for enrollment onto the study.

Submit agent requests through the Pharmaceutical Management Branch (PMB) Online Agent Order Processing (OAOP) application. Access to OAOP requires the establishment of a CTEP IAM account and the maintenance of an “active” account status, a “current” password, and active person registration status. For questions about drug orders, transfers, returns, or accountability, call or email PMB any time. Refer to the PMB’s website for specific policies and guidelines related to agent management.

8.1.3.1 Agent Inventory Records – The investigator, or a responsible party designated by the investigator, must maintain a careful record of the receipt, dispensing and final disposition of all agents received from the PMB using the appropriate NCI Investigational Agent (Drug) Accountability Record (DARF) available on the CTEP forms page. Store and maintain separate NCI Investigational Agent Accountability Records for each agent, strength, formulation and ordering investigator on this protocol.

### 8.1.4 Investigator Brochure Availability

The current versions of the Investigator’s Brochures (IBs) for the agents will be accessible to site investigators and research staff through the PMB OAOP application. Access to OAOP requires the establishment of a CTEP IAM account and the maintenance of an “active” account status, a “current” password, and active person registration status. Questions about IB access may be directed to the PMB IB Coordinator via email.

## 9 STATISTICAL CONSIDERATIONS

### 9.1 Study Design/Endpoints

The dose escalation component of this study is a dose-escalation trial of Telaglenastat (CB-839) HCl and Osimertinib (AZD9291) in patients with metastatic *EGFR* activating mutation positive NSCLC. It has been designed to define the RP2D of Telaglenastat (CB-839) HCl and Osimertinib (AZD9291). Assuming DLT rate is as few as 30% at MTD, a traditional 3+3 dose escalation design will be adopted and 3-6 evaluable patients will be treated at each dose level. Dose escalation rules are defined in Section 6.2. An evaluable patient for a DLT is defined as the patient who must have started the combination therapy portion of the study. Patients who discontinue combined treatment during the 28-day evaluation period for any reason other than treatment-related or dose-limiting toxicity will not be evaluable. Non-evaluable patients will be replaced. Nine to eighteen patients are expected to be enrolled depending on the number of dose escalations and assuming that a total of 6 patients will be treated at the final RP2D level. The DLT period will be set at 28 days of combination therapy.

In the 10 patient expansion cohort, we will gain additional experience and understanding regarding the safety, tolerability, and efficacy of combination Telaglenastat (CB-839) HCl and Osimertinib (AZD9291) in patients with *EGFR* activating mutation positive NSCLC who have progressed on first line *EGFR* TKI with osimertinib.

In the expansion cohort component of the study, a safety monitoring scheme will also be implemented by including a stopping rule based on the number of DLTs among the first 10 patients in the expansion cohort. Enrollment may be paused if the lower bound of the 1-sided 80% exact binomial confidence interval of the estimated DLT excludes 30%. After the first 10 patients have been evaluated for DLT, the study will be stopped for safety if at least 5 patients with DLTs are observed. The study will continue if no more than 4 patients experience DLTs.

Integral testing for *EGFR* status will be completed locally but an integrated *EGFR* test will also be completed centrally for confirmation of *EGFR* status. In case a patient is deemed to be *EGFR* mutant by the local test but *EGFR* wild-type by the central test, that patient will not be included in the primary analysis.

All toxicities will be summarized as the percentage of patients experiencing each type and grade of event according to dose level. Patients who receive at least one dose of treatment will be included in the analysis.

The ORR will be calculated as the proportion of patients who achieve a response to therapy divided by the total number of evaluable patients. An evaluable patient is defined as an eligible patient who has received at least one dose of therapy and has centralized confirmation of positive *EGFR* mutation status. All evaluable patients will be included in calculating the ORR for the study along with corresponding 95% binomial CIs (assuming that the number of patients who respond is binomially distributed). Separately, all patients treated at the RP2D in either the dose expansion or the expansion cohort will be analyzed.

Definition of Primary Endpoints

- Safety, tolerability and RP2D of combination therapy with Telaglenastat (CB-839) HCl and Osimertinib (AZD9291) in patients with metastatic *EGFR* activating mutation positive NSCLC.

Definition of Secondary Endpoints

- DLTs as assessed by CTCAE version 5.0 of the combination of Telaglenastat (CB-839) HCl and Osimertinib (AZD9291) in patients with metastatic *EGFR* activating mutation positive NSCLC.
- PFS of patients with metastatic *EGFR* activating mutation positive NSCLC who have progressed on front-line *EGFR* inhibitor therapy following treatment with Telaglenastat (CB-839) HCl and Osimertinib (AZD9291). PFS is defined as the time from initiation of therapy to documented progression or death without progression.
- OS of patients with metastatic *EGFR* activating mutation positive NSCLC who have progressed on front-line *EGFR* inhibitor therapy following treatment with Telaglenastat (CB-839) HCl and Osimertinib (AZD9291). OS is defined as the time from initiation of therapy to death from any cause.

Definition of Correlative Endpoints

- Post-Telaglenastat (CB-839) HCl PK as assessed by Telaglenastat (CB-839) HCl drug levels following both single agent therapy as well as combination therapy with Telaglenastat (CB-839) HCl and Osimertinib (AZD9291) in patients with metastatic *EGFR* activating mutation positive NSCLC.
- Post-Osimertinib (AZD9291) PK as assessed by Osimertinib (AZD9291) drug levels following combination therapy with Telaglenastat (CB-839) HCl and Osimertinib (AZD9291) in patients with metastatic *EGFR* activating mutation positive NSCLC.  
Changes in *EGFR* mutational status as assessed by cfDNA in patients with metastatic *EGFR* activating mutation positive NSCLC who have progressed on front-line *EGFR* inhibitor therapy.
- Changes in circulating levels of glutamine, glutamate, aspartate, and asparagine as assessed by plasma concentrations of these compounds in patients with metastatic *EGFR* activating mutation positive NSCLC who have progressed on front-line *EGFR* inhibitor therapy.

## 9.2 Sample Size/Accrual Rate

This study plans to accrue a minimum of 9 and a maximum of 28 patients. Estimated accrual rate is 5 patients/month.

NCI Protocol #: 10216  
Version Date: 09/17/2024  
Sample Size Justification:

For the dose escalation portion of the study, the trial will be conducted using a standard 3+3 dose escalation design. As there are three dose levels to be assessed, a total of 9 to 18 patients are expected to be enrolled depending on the number of dose escalations and assuming that a total of 6 patients will be treated at the final MTD/RP2D level.

In the expansion cohort component of the study, we plan to obtain additional data regarding safety and tolerability as well as preliminary efficacy of combination CB-839 and osimertinib. With a total of 16 patients at MTD/RP2D (6 + 10), we will estimate the ORR with a 95% confidence interval half-width of less than 25.4%, using the Clopper-Pearson exact method.

### PLANNED ENROLLMENT REPORT

This patient population represents a fraction of the entire NSCLC population, especially since this study is limited to the second line setting. Given the small numbers involved in this study, it is impossible to predict precise accrual patterns, but they should be reflective of the demographic areas of each accruing center. All patients with metastatic NSCLC who meet eligibility criteria will be eligible for this study.

Racial Categories	Ethnic Categories				Total
	Not Hispanic or Latino		Hispanic or Latino		
	Female	Male	Female	Male	
American Indian/ Alaska Native	0	0	0	0	0

Racial Categories	Ethnic Categories				Total
	Not Hispanic or Latino		Hispanic or Latino		
	Female	Male	Female	Male	
Asian	1	2	0	0	3
Native Hawaiian or Other Pacific Islander	1	0	0	0	1
Black or African American	1	1	0	0	1
White	10	5	3	2	15
More Than One Race	1	0	0	1	2

Total	14	8	3	3	22
-------	----	---	---	---	----

PHS 398 / PHS 2590 (Rev. 08/12 Approved Through 8/31/2015)

OMB No. 0925-0001/0002

### 9.3 Stratification Factors

This is a non-randomized study and therefore no stratification will be performed.

### 9.4 Analysis of Secondary and Exploratory Endpoints

Frequency and severity of AEs and tolerability of the regimen will be collected and summarized by descriptive statistics. The maximum grade for each type of toxicity will be recorded for each patient, and frequency tables will be reviewed to determine toxicity patterns. All patients who have received at least one dose of the therapeutic agents will be evaluable for toxicity and tolerability.

We will explore PK endpoints such as  $C_{ss}$ , AUC,  $C_L$ ,  $V_d$ , and  $t_{1/2}$  computed using non-compartmental and compartmental methods. We will use graphical analyses as well as repeated measure models (linear or nonlinear mixed models, generalized estimating equations [GEE]) to assess the PK and PD markers described above in relation to clinical treatment outcomes, recognizing some inherent limitations due to sample size.

OS will be defined as time from initiation of therapy to death. PFS will be defined as the time from initiation of therapy to the time of RECIST progression or death. Survival will initially be modeled using Kaplan-Meier methods, resulting in median survival times with 95% CI, assuming sufficient events have occurred.

All exploratory studies will be performed on specimens obtained from patients treated at MTD including the expansion cohort portion of the study. Graphical analyses will be largely used to assess potential patterns and relationships. cfDNA and circulating levels of glutamine, glutamate, aspartate, and asparagine will be summarized at baseline, after one month of treatment, and at time of progression. All continuous measurements will be summarized using mean +/- SEM, range, and median at each time point. Changes in these measurements from baseline to after treatment, or baseline to progression will be assessed using paired Wilcoxon tests. Adjustments for multiple comparisons or multiple outcomes will be performed using Bonferroni correction.  $^{18}\text{F}$ -FDG-PET parameters will also be summarized at baseline and after treatment using mean +/- SEM, range, and median. The changes in the FDG-PET/CT parameter measurements from baseline to after treatment will be compared between responders and non-responders using two sample t-test or Wilcoxon test, whichever is appropriate. Fisher's exact test will be used to assess the association between biomarkers, genetic alterations and response to study drugs. Logistics regression model might also be used to identify potential predictive and prognostic biomarkers beyond any genomic alteration with response to study drugs. Initially, data will be presented as summary statistics and upon sufficient accrual, a more detailed analytical plan will be developed. Given the small sample size, these analyses will be dependent on there being a sufficient number of responders with samples available.

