#### 2.2.2.3.1 Clinical PK and Pharmacodynamics

Osimertinib (AZD9291) PK parameters have been characterized in healthy subjects and NSCLC patients (Osimertinib (AZD9291) Investigator's Brochure, 2018). Based on population PK analysis, Osimertinib (AZD9291) apparent plasma clearance is 14.3 L/h, apparent volume of distribution is 918 L, and  $t_{1/2}$  is approximately 44 hours. The area under the plasma concentration-time curve (AUC) and maximum serum concentration ( $C_{max}$ ) of Osimertinib (AZD9291) increased dose proportionally over 20 mg to 240 mg dose range (0.25 to 3 times the recommended dosage) after PO administration and exhibited linear PK. Administration of Osimertinib (AZD9291) PO QD resulted in approximately 3-fold accumulation with steady state exposures achieved after 15 days of dosing. At steady state, the  $C_{max}$  to minimal serum concentration ( $C_{min}$ ) ratio was 1.6-fold. The median time to  $C_{max}$  of Osimertinib (AZD9291) was 6 hours (range 3 to 24 hours). The absolute bioavailability of Osimertinib (AZD9291) is 70% (90% confidence interval [CI] 67, 73). Neither food nor gastric pH affects the exposure of Osimertinib (AZD9291).

Based on clinical drug-drug interaction (DDI) studies, interactions with strong CYP3A4 inhibitors are unlikely but strong CYP3A4 inducers can decrease the exposure of (Osimertinib (AZD9291) Investigator's Brochure, 2018). Osimertinib (AZD9291) may also increase the exposure of co-administered breast cancer resistance protein (BCRP) substrates. Clinical PK interactions with co-administered CYP3A4 substrates are unlikely. No clinically significant differences in the PK of Osimertinib (AZD9291) were observed based on age, sex, ethnicity, body weight, smoking status, mild or moderate or severe renal impairment (creatinine clearance [CLcr]  $>15$  mL/min by Cockcroft- Gault) or mild or moderate hepatic impairment (mild: Child Pugh A or total bilirubin less than or equal to the upper limit of normal [ULN] and AST greater than ULN or total bilirubin between 1 to 1.5 times ULN and any AST; moderate: Child Pugh B or total bilirubin between 1.5 to 3 times ULN and any AST).

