#### 2.4.6 Cell-Free DNA Analysis (Exploratory)

cfDNA will be assessed for *EGFR* mutational status, T790M mutational status and resistance mechanisms at different time points in this study. Peripheral blood will be collected for cfDNA at baseline, after one month of treatment, and at time of progression. In the phase 1 study, cfDNA will also be collected on C1D15 after single agent Telaglenastat (CB-839) HCl prior to initiation of combination therapy. cfDNA for *EGFR* status will be compared with archival/baseline specimen for concordance. Blood based assays for detection of resistance mechanisms are widely used in clinical practice, and have also yielded information about resistance mechanisms to treatment (Blakely *et al.*, 2017).

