## 6 TREATMENT PLAN

### 6.1 Agent Administration

Treatment will be administered on an outpatient basis. Reported AEs and potential risks are described in Section 10. Appropriate dose modifications are described in Section 7. No investigational or commercial agents or therapies other than those described below may be administered with the intent to treat the patient's malignancy.

**Dose Escalation Treatment Plan:** A single arm dose escalation portion of the study will first be performed to determine the optimal dosing strategy where three dose levels will be assessed. Extensive PK studies will also be conducted to assess for any potential drug-drug interactions through the obtaining of peripheral blood. Eligible patients will initially receive treatment with single agent Telaglenastat (CB-839) HCl BID according to the dose escalation strategy and PK sampling will be done on Day 15. Starting on Day 16, patients will then go on to receive both Osimertinib (AZD9291) 80 mg PO QD as well as Telaglenastat (CB-839) HCl PO BID at the same dose as initially provided during the monotherapy portion of the study and a second set of PK analyses will be conducted on Day 1 of Cycle 2 for both Osimertinib (AZD9291) and Telaglenastat (CB-839) HCl (see table below). Peripheral blood will also be obtained for a PK assessment at the beginning of each 28- day treatment cycle starting with Cycle 2. An assessment for response to treatment will be conducted with a CT of the chest, abdomen, and pelvis (C/A/P) every 2 months as is standard practice.

Patients will continue to receive treatment until the time of disease progression, unacceptable toxicity, or treatment is discontinued based on patient/physician preference.

Patients enrolled to the dose escalation portion of the study will be treated according to a dose escalation schedule where three different dose levels will be assessed. For all dose levels, the Osimertinib (AZD9291) dose will be set at 80 mg PO QD. The dose levels of Telaglenastat (CB-839) HCl are as follows:

1) 400 mg PO BID; 2) 600 mg PO BID; 3) 800 mg PO BID. Dose Level -1 will be 200 mg Telaglenastat (CB- 839) HCl BID.

Phase 1 Dose Escalation Schedule		
Dose Level	Dose*	
	Telaglenastat (CB-839) HCl (mg) orally BID	Osimertinib (AZD9291) (mg) orally daily
Level -1	200 mg	80 mg
Level 1 (Starting Dose)	400 mg	80 mg
Level 2	600 mg	80 mg
Level 3	800 mg	80 mg

BID = twice daily, QD = once daily  
\*Dosing is given orally on a continuous schedule

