c: Albumin, alkaline phosphatase, total bilirubin, bicarbonate, blood creatine phosphokinase, BUN, calcium, chloride, creatinine, glucose, LDH, magnesium, phosphorus, potassium, total protein, SGOT [AST], SGPT [ALT], sodium. Important note: In case a subject shows an AST or ALT  $\geq 3 \times \text{ULN}$  or total bilirubin  $\geq 2 \times \text{ULN}$  please refer to Appendix E ‘Actions Required in Cases of Increases in Liver Biochemistry and Evaluation of Hy’s Law’, for further instructions.

\* Electrolyte abnormalities (hypokalaemia, hypomagnesaemia, hypocalcaemia) must be corrected to be within normal ranges prior to first dose and electrolyte levels monitored during study treatment.

d: To be repeated if clinically indicated

e: Serum pregnancy test (women of childbearing potential).

f: Off-study evaluation.

g: Peripheral blood and plasma for cfDNA and oncometabolite studies will be collected at baseline, C1D15 (escalation only), C2D1, and progression.

h: Peripheral blood samples for dose escalation cohort PK analysis will be collected at the following timepoints: 1) baseline/pre-dose; 2) C1D15 before the morning dose of Telaglenastat (CB-839) HCl (0 min) and at 30 min, 1 hour, 2 hours, 4 hours, and 8 hours following this dose; and 3) C2D1 before the morning dose of Telaglenastat (CB-839) HCl and Osimertinib (AZD9291) (0 min) and at 30 min, 1 hour, 2 hours, 4 hours, and 8 hours following this dose. A 24 hour (C2D2, pre-dose) PK collection is optional but encouraged (escalation cohort only). Peripheral blood samples (baseline / 0 hours) will also be collected on Day 1 of each treatment cycle starting with Cycle 3. There is no window for pre-dose research labs as long as done on the same calendar day. Window for post-dose labs is +/- 15 minutes.

i: Peripheral blood samples for phase 2 PK analysis (baseline / 0 hours) will be collected at baseline and on Day 1 of each treatment cycle starting with Cycle 2.

j: To be performed during screening end of treatment. Per the FDA label, echocardiogram is indicated at baseline and during treatment for patients with cardiac risk factors, or if clinically indicated.

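### The exploratory C2D1 change combines patients with 13 days and patients with 28 days on the combination, and Section 9.4 does not split them by cohort

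*Combined protocol and SAP*

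**What the plan says.** **Analysis set and test.** Section 9.4 states: "All exploratory studies will be performed on specimens obtained from patients treated at MTD including the expansion cohort portion of the study". For these specimens, "cfDNA and circulating levels of glutamine, glutamate, aspartate, and asparagine will be summarized at baseline, after one month of treatment, and at time of progression". The test is then given: "Changes in these measurements from baseline to after treatment, or baseline to progression will be assessed using paired Wilcoxon tests". The section contains no by-cohort summary, no cohort term and no exposure variable.

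**Sampling.** Footnote g of the study calendar (Section 11.1) reads: "Peripheral blood and plasma for cfDNA and oncometabolite studies will be collected at baseline, C1D15 (escalation only), C2D1, and progression". Section 2.4.6 describes the cfDNA schedule as "Peripheral blood will be collected for cfDNA at baseline, after one month of treatment, and at time of progression", which makes C2D1 the one-month draw. The specimen tables in Sections 5.1.1 and 5.1.2 place that draw before the C2D1 dose in both cohorts.

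**Dosing.** In escalation, Section 6.1 gives telaglenastat alone first, and then: "Starting on Day 16, patients will then go on to receive both Osimertinib (AZD9291) 80 mg PO QD". Calendar footnote b repeats the Day 16 start. In expansion, the regimen table in Section 6.1 and the expansion row of the calendar have osimertinib running from Day 1. The cycle is 28 days in both parts.

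**Purpose.** Section 5.10.1 says the metabolite samples are meant to show changes under telaglenastat alone or under the combination.

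**The concern.** The label 'one month' is accurate as time since first protocol dose in both cohorts, but not as time on the combination. The two schedules reach C2D1 with different histories. Escalation patients have had 15 days of telaglenastat alone, with no EGFR inhibitor because Section 6.1 allows no other anticancer agent, and then 13 days of both drugs. Expansion patients have had 28 days of both.

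A paired test controls for each patient's baseline. It does not account for a different exposure between baseline and the second sample. Schedule also coincides entirely with cohort, so one combined C2D1 change cannot show whether a result, or its absence, reflects the combination or the mix of schedules.

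cfDNA is the most exposed because it is used to follow EGFR and T790M status, which bears directly on osimertinib. The only sample that isolates the monotherapy effect, C1D15 in escalation, is collected but is not among the time points that Section 9.4 summarises.

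**Working it through.** **The plan's own figure.** The plan states no count of combination days at C2D1. The nearest figure for the same patients is in Section 9.2: 16 patients (6 + 10) and a 95% Clopper-Pearson half-width for the ORR below 25.4%. The widest interval for n = 16 is at 8 responders, with limits 24.65% and 75.35%. The half-width is (75.35 − 24.65)/2 = 25.35%. The figure reproduces and is not in dispute.

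**Inputs**
- Cycle length: 28 days (Section 6.1).
- Osimertinib start: Day 16 in escalation, Day 1 in expansion (Sections 6.1 and 11.1).
- Telaglenastat start: Day 1 in both.
- Patients: 6 escalation and 10 expansion (Section 9.2).
- Visit window: ±5 days (Section 11.1, footnote a).

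**Dosing days before the pre-dose C2D1 sample** = 28 − start day + 1

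| | Escalation | Expansion |
|---|---|---|
| Combination | 28 − 16 + 1 = 13 | 28 − 1 + 1 = 28 |
| Telaglenastat | 28 | 28 |

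**Mixture.** The escalation share is 6/16 = 37.5%. The mean time on the combination is (6 × 13 + 10 × 28)/16 = 358/16 = 22.4 days, which describes neither cohort.

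**Visit window.** Moving C2D1 alone by ±5 days gives 8 to 18 days in escalation and 23 to 33 in expansion, with no overlap. If Day 16 also moves by 5 days the other way, escalation spans 3 to 23 days and meets the expansion range only at its extreme.

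**Can an existing escalation sample be matched?** Escalation patients complete 28 combination days before the dose on study day 16 + 28 = 44, which is Cycle 2 Day 16. No cfDNA or metabolite sample is planned then, so re-labelling visits cannot align the cohorts.

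**Drug level or duration?** Section 2.2.2.3.1 gives a half-life of about 44 hours and has "steady state exposures achieved after 15 days of dosing". Thirteen days is 13 × 24/44 = 7.1 half-lives, or 1 − 0.5^7.1 ≈ 99.3% of steady state; 15 days gives about 99.7%. The cohorts differ in duration of exposure, not materially in osimertinib level.

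**What a separate escalation test could show.** With n = 6, the smallest two-sided exact signed-rank p is 2 × 0.5^6 = 0.031. Section 9.4 uses Bonferroni without defining the family. If the family is assumed to be the four metabolites, the level is 0.05/4 = 0.0125, which six patients cannot reach.

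**The case against.** **Pooling is inferred.** Section 9.4 says which specimens are used and never says outright that the cohorts enter one test. It expects graphs to carry most of the analysis and promises a fuller plan later. That is fair. Still, one set, common time points and one test with no split lead to pooling if followed as written, and the promised fuller plan is the natural place to settle it.

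**Metabolites are less affected.** Section 5.8 gives the assay's purpose as measuring telaglenastat's pharmacodynamic effect, and both cohorts have had 28 days of that drug at C2D1. The documents give no evidence that osimertinib duration alters plasma glutamine or the related metabolites. This stands, and it limits the point mainly to cfDNA.

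**Stronger readings that the documents do not support**
- *A reader might infer a steady-state shortfall*, since 13 is below 15. At about 99% of steady state there is none of consequence.
- *A reader might infer that C2D1 Css is pooled in the same way.* The PK paragraph of Section 9.4 names no population. PK is a secondary objective (Section 1.2) and an integrated study (Section 2.4.4), so the sentence on exploratory specimens does not clearly govern it.
- *A reader might infer that PFS and OS are distorted by the lead-in.* Section 9.1 says "PFS is defined as the time from initiation of therapy to documented progression or death without progression", and Sections 9.4 and 12.1.6 agree. Timing from first protocol therapy is a legitimate and consistent choice, and no text places PFS on this 16-patient specimen set.
- *A reader might infer a spurious treatment effect.* None is demonstrated. The tests are within-patient and exploratory, and no decision depends on them.

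**Conclusion.** The point holds in a limited form. As written, the single C2D1 change combines 13-day and 28-day exposures to the combination, with the shorter exposure in 6 of 16 patients. The consequence is interpretive: a pooled cfDNA change at C2D1 cannot be read as the effect of a month on the combination.

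This rests on three assumptions: that the absence of a stated split means pooling, that the planned 6 + 10 patients all supply paired samples, and that visits fall near their nominal days. Missing samples would change the 37.5% share but not the 13-versus-28 contrast.

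Severity is minor. The endpoints are exploratory, and the primary safety and RP2D conclusions and the ORR estimate are unaffected. It is a cheap improvement.

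**What to change.** In Section 9.4, or in the more detailed analytical plan it announces:

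1. Derive days since first combination dose for every exploratory sample, from actual dosing and sampling dates.
2. Present C2D1 changes in cfDNA and metabolites descriptively by cohort, beside any pooled result, and label C2D1 by days on the combination.
3. If a pooled paired test is kept, stratify it by cohort. Do not add a separate escalation test, which six patients cannot make informative.
4. Add the escalation C1D15 sample to the summary as the monotherapy time point, to meet the aim in Section 5.10.1. Section 5.3.3 omits C1D15 from the metabolite collection times, while Sections 5.1.1, 5.8 and 11.1 include it. Reconcile these, and confirm which samples exist.

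The cost is one derived variable, some wording and a few more tables. Escalation results (n = 6) will be descriptive only. No new visit or specimen is needed. The Summary of Changes records accrual as permanently closed, so the mismatch has to be handled in the analysis.
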